Pharmacokinetics: Quinacrine is usually administered orally with a full glass of water after a meal [26, 32, 33, 35, 43-45]. It is absorbed quickly after oral administration with plasma levels increasing 2-4 hours after administration and reaching a peak in 8-12 hours [26, 46, 47]. Plasma concentration increases fast during the first week and equilibrates by the fourth week [48, 49]. The highest concentrations of quinacrine are found in the liver, spleen, lungs, and adrenal glands, lowest are found in the brain, heart, and skeletal muscle [47]. Concentration in the liver may be 20,000 times that in the plasma [50]. Quinacrine is deposited in the skin, fingernails and hair [26]. The drug crosses the placental barrier and, concentrations in fetal tissue are similar to maternal concentrations [51, 52]. Cerebrospinal fluid concentrations are 1 to 5% of corresponding plasma level [47]. 80-90% of the drug is bound to plasma proteins when given at therapeutic doses. Half-life of the drug is 5-14 days depending on the dosing regimen [48, 53]. Excretion of quinacrine occurs principally through the urine where less than 11% is eliminated daily. Small amounts are excreted in bile, sweat, saliva and breast milk [47]. Elimination via the renal system may be enhanced by acidification and reduced by alkalization [26, 46, 47]. Quinacrine may be detected in the urine up to 2 months after therapy has been discontinued.

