The safety and bioavailability of quinacrine make it an attractive agent for use in combinatorial therapy. Quinacrine's long-term safety has been demonstrated in patients with chronic diseases, such as rheumatoid arthritis and malaria; patients have taken daily quinacrine for months at a time to control their symptoms, with few side effects. As previously mentioned, the pharmacokinetics and safety of quinacrine have been extensively studied as it was administered as a protective measure to millions of US soldiers in the Pacific region during World War II. Some of the more serious side effects of quinacrine are mild in comparison to other anti-cancer chemotherapeutics and most of the conditions can be easily reversed after treatment cessation or dose reduction. Many of quinacrine's side effects develop gradually, starting from minor lesions in the case of dermatitis or a slight decrease in blood counts in the development of anemia, and have been found to be completely and easily reversible, if quinacrine use is discontinued at this early stage [2]. In our lab work, the minimal weight loss caused by the quinacrine combinatorial therapies was reversed upon cessation of treatment. Some of the side effects exhibited due to quinacrine treatment can be used in the clinical setting to confirm proper dosing of the drug in the treatment of cancer patients. The yellow discoloration of the skin due to the accumulation of the bright yellow compound would indicate to the clinician that the drug has reached the equilibrium and as in the case of squamous cell carcinomas, has potentially reached areas where tumor has developed [58].

Figure 2: Quinacrine delays tumor growth and enhances the effects of 5-FU in vivo. Effect of quinacrine/5-FU combinatorial therapy on HT-29-luc (A), DLD-1 (B) and RKO (C) xenografts in nu/nu mice ($n = 3-5/group \pm s.d.$). Quinacrine was administered via oral gavage every 48 h, 5-FU was given intraperitoneally once a week. (D) Tumor delay in days necessary for a tumor to reach a volume 5 times greater than the initial volume (or 10 times the bioluminescent signal). (E) Effect of combinatorial therapy on the body weight of the mice of all 3 xenograft experiments ($n = 13-15/group \pm s.d.$) [4].

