3.0 STUDY DESIGN

3.1 Phase I

Because of the well published safety profiles of both quinacrine and capecitabine, the Phase I portion of our study will aim to determine the tolerability of both agents in combinations when used at established clinical doses. Given that capecitabine is considered as standard treatment for mCRC, a full dose of 1000mg/m² orally bid of capecitabine will be administered with different doses of quinacrine. The maximum dose of quinacrine to be tested is 200 mg bid. The first patient in this study will be treated with 1000 mg/m² orally bid of capecitabine on days 1-14, and a starting dose of 100 mg orally daily of quinacrine on days 1-21 of a 21 day cycle (dose level -2 in table below). All patients will be evaluated for baseline toxicity. Toxicity will be evaluated according to the National Cancer Institute Common Toxicity Criteria (current version 4.0).

A modified version 4B of Simon's accelerated titration design (Figure 3) will be used in the Phase I portion of our study to limit the number of patients treated at potentially sub therapeutic doses [60]. In this design, a cohort has at least one patient treated at a dose level (designated as "i"). If no DLT is observed (i.e. no toxicity, T, >2) at cycle 1, another single-patient cohort is treated with the next higher dose level (i.e., "Add 1 to i"). On the other hand, if a DLT is observed in a single- patient cohort in the first cycle, an additional two patients are treated at the same dose level (i.e. Dose i 2 patients). If another instance of toxicity > grade 2 is observed, three additional patients will be treated at that dose level. If at most 2 of the 6 patients treated at a dose level experience a DLT, that dose level is identified as the MTD.

Dose Escalation		
	Dose *	
Dose Level	Quinacrine (mg)	Capecitabine (mg/m2)
Level -2	100, qd	1000 bid

Level -1	100, bid	1000 bid
Level 0	200, bid	1000 bid

Adopting the modified version 4B of Simon's accelerated titration design, it is possible that only three patients are enrolled in Phase I. This situation can occur in the event that the first patient that received dose level -2, the first patient that received dose level -1 and the first patient that received dose level 0 do not experience toxicity>2.

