*NA indicates that the action taken is the same regardless of whether there were patients previously treated at a higher dose

The MTD will be used at recommended phase 2 dose (RP2D) unless there are any safety concerns. Patients who needed a dose reduction after being treated with RP2D in phase I will receive the reduced dose in phase II.

For the purposes of quinacrine dose escalation, the dose-limiting toxicities (DLT) that will be taken into account include toxicity grade >2 hematological, GI/diarrhea, skin, LFT abnormality or otherwise unexpected grade 3 toxicity or higher, associated with the combination therapy. Quinacrine dose modifications will not be made in the event of toxicities that are primarily attributed to capecitabine; namely, > grade 2 alopecia and hand and foot syndrome (HFS). Patients experiencing DLT will be permitted to continue their treatment after a single step dose reduction.

Intra-patient dose escalation will occur only for patients experiencing Common Toxicity Criteria < grade 2 toxicity on a previous course. The intra-patient dose escalation for a patient in lower level dose cohort will be on hold until the highest dose cohort patient completes first cycle of therapy. For purposes of toxicity assessment, patient response to the initial dose received will be considered. Total time in therapy, however, will be adjudged to include the whole duration the patient received treatment, regardless of the doses received.

General concomitant medications, dose adjustment, drug warnings and supportive care guidelines, duration of therapy, duration of follow up, and criteria for removal from treatment, as described throughout the protocol will be applied to both Phase I and II.

The endpoint of the Phase I portion of this study will occur when the safety and tolerability of the quinacrine-capecitabine combination is evaluated. Based on our preclinical data and the history of use of both capecitabine and quinacrine, we expect that the following regimen will be safely tolerated by the majority of patients.

	Premedications;				Cycle
Agent	Precautions	Dose	Route	Schedule	Length
Quinacrine	After a meal with a	200 mg tablets	Orally:	Daily on	
	glass of water	Orally twice a	at least 8 hours	Days 1-21	
		day	between each		
			dose		
Capecitabine*	Within 30 minutes	1000 mg/m ²	Orally:	Daily on	21 days
	after a meal with	Orally twice a	at least 8 hours	Days 1-14	(3 weeks)
	water	day	between each		
			dose		

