*The calculated total daily capecitabine dose by body surface area (BSA) will be rounded down to allow doses using 500mg tablets

After finishing cycle #1, start cycle #2 on day 22, and continue every 21 days.

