8. CORRELATIVE/SPECIAL STUDIES

8.1 Laboratory Correlative Studies

8.1.1 Pharmacokinetic (PK) study

Pharmacokinetic information including Cmax, T1/2(half-life) and AUC of investigational drugs capecitabine and quinacrine will be collected as exploratory objectives of phase I and II parts of the study. Given linear kinetics of quinacrine, and a short half-life (4hrs) from previous human study data, blood sample for pharmacokinetic (PK) analysis in this study will be collected on 5 different time points on day 1 of cycle 1, and on day 1 of cycle 2 and cycle 3. For pharmacokinetic analysis, 4.5mL of blood will be drawn into a lithium heparin tube at each time point.

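### The only stated DLT window is cycle 1 (21 days); on section 1.4's accumulation figures it closes at about 65–95% of plateau, and the multi-patient tallies behind the MTD have no stated window

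*Combined protocol and SAP*

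**What the plan says.** Section 3.1 gives the basic escalation step as "If no DLT is observed (i.e. no toxicity, T, >2) at cycle 1, another single-patient cohort is treated with the next higher dose level". The companion step, adding two patients after a DLT in a single-patient cohort, is also limited to the first cycle. No time limit is attached to the 3- and 6-patient tallies in the section 3.1 text, to Figure 3, to the decision chart, to the DLT definition or to section 11.1.

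Under the chart, one patient without a DLT at level 0 makes level 0 the MTD, and section 3.1 notes that Phase I may end with three patients. The MTD then goes forward: "The MTD will be used at recommended phase 2 dose (RP2D) unless there are any safety concerns".

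The first patient receives "a starting dose of 100 mg orally daily of quinacrine on days 1-21 of a 21 day cycle". No loading dose is stated, and dosing runs on without a break: "After finishing cycle #1, start cycle #2 on day 22, and continue every 21 days".

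The documents give two accounts of quinacrine's kinetics.

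- Section 1.4: "Plasma concentration increases fast during the first week and equilibrates by the fourth week", and "Half-life of the drug is 5-14 days depending on the dosing regimen".
- Section 8.1.1, justifying the PK sampling times: "Given linear kinetics of quinacrine, and a short half-life (4hrs) from previous human study data".

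Section 1.5 adds: "Many of quinacrine's side effects develop gradually". Appendix A says PK samples are assayed in batches at the end of the study, so they cannot show accumulation while escalation is under way.

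**The concern.** On section 1.4, the stated window ends just before or well before the drug levels off, depending on where in the range the half-life lies. Even the most favourable reading of the fourth week, its first day (day 22), falls after day 21. No section explains why 21 days is enough.

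Late toxicity is plausible on the protocol's own account. Section 1.5 names dermatitis and falling blood counts as effects that build up gradually, and section 7.3 links hepatitis to prolonged high-dose use. Skin, hematological and liver-function abnormalities are all named DLT categories in section 3.1.

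At stake is the dose carried into up to 29 Phase II patients. It could rest on one patient observed for 21 days at the top level. For levels with 3 or 6 patients, the text does not say whether a DLT in cycle 2 counts.

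**Working it through.** **1. The plan's own figures.** Let p be the chance of T > 2 in a patient and q = 1 − p. The chance of escalation is q + p·q². At p = 0.30 this is 0.70 + 0.30 × 0.49 = 0.847, which matches section 11.1. All nine columns of the four tabulated rows reproduce to three decimals. The Phase II toxicity rule also reproduces: 80.5% halted at a true DLT rate of 33.3%, and 6.3% at 15%. The arithmetic is not in question; what matters is the period over which p is observed.

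**2. Accumulation on section 1.4.** The documents give no percentage of plateau at day 21, so I assume one-compartment linear kinetics with constant dosing. With half-life h days and k = ln 2 / h:

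- level at day t as a fraction of plateau: 1 − 2^(−t/h)
- mean over days 1–21: 1 − (1 − e^(−21k)) / (21k)
- mean over days 22–42: 1 − (e^(−21k) − e^(−42k)) / (21k)
- further rise after day 21: 1 / (level at day 21) − 1

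For h = 5, the day-21 level is 1 − 2^(−4.2) = 0.946. For h = 14, it is 1 − 2^(−1.5) = 0.646. Discrete once-daily and twice-daily dosing give the same day-21 fractions.

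| Half-life | Level at day 21 | Mean, cycle 1 | Mean, cycle 2 | Further rise after day 21 |
|---|---|---|---|---|
| 5 d | 94.6% | 67.5% | 98.2% | 5.8% |
| 7 d | 87.5% | 57.9% | 94.7% | 14.3% |
| 10 d | 76.7% | 47.3% | 87.7% | 30.4% |
| 14 d | 64.6% | 37.8% | 78.0% | 54.7% |

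Mean exposure in cycle 2 is 98.2/67.5 ≈ 1.5 to 78.0/37.8 ≈ 2.1 times that in cycle 1.

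**3. Consistency within section 1.4.** If equilibrium is taken to mean 90% of plateau (my assumption), reaching it between days 22 and 28 implies h = 22 × ln 2 / ln 10 = 6.6 d to 28 × ln 2 / ln 10 = 8.4 d. Day 21 is then at about 89% to 82%, and the cycle 1 mean is about 60% to 52%. A 14-day half-life gives only 75% at day 28, which fits the fourth-week statement poorly.

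**4. Accumulation on section 8.1.1.** With h = 4 hours, 95% of plateau is reached in 4 × log₂ 20 ≈ 17 hours, and day 21 is at 100%. The two half-lives differ by a factor of 120/4 = 30 to 336/4 = 84.

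**5. What under-counting would do.** This is an illustration only; the documents give no exposure–toxicity relation. Suppose the eventual DLT risk is 30% and cycle 1 reveals 95%, 80% or 65% of it. Then p in cycle 1 is 0.285, 0.24 or 0.195, and the chance of escalation rises from 84.7% to 86.1%, 89.9% or 93.1%.

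**The case against.** Several stronger readings are tempting, and the documents do not support them.

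- **That each dose is cleared far below plateau.** At the end of the window this is true only for the longer half-lives. At 5 days the level is 95%, and at half-lives that fit the fourth-week statement it is about 82–89%. Section 1.4 says the half-life depends on the regimen, and nothing shows that 14 days applies here. The larger shortfall appears in the cycle average.
- **That a DLT in cycle 2 counts toward no Phase I decision.** The first-cycle limit is written only for the single-patient steps. For the larger tallies the window is unspecified, which is a different defect.
- **That the safety-concerns clause is the sole protection.** The section 11.1 rule halts Phase II at 5 DLTs in the first 10 patients or 8 in 29, with no cycle limit. Section 5.1 provides holds and reductions, section 11.2 anticipates a dose reduction after six patients, and section 12.2 allows board review.
- **That the tabulated p(T>2) values describe a reduced exposure.** They are a hypothetical grid from 0.1 to 0.9 and are not tied to any exposure.

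The strongest objection is section 8.1.1: on a 4-hour half-life the issue vanishes. Other statements in section 1.4 sit more easily with slow elimination (less than 11% eliminated daily in urine, and detection there up to two months after stopping). Only the sponsor can settle which figure applies.

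Section 1.5 also gives no timescale for gradual effects and calls them reversible if the drug is stopped early. The size of any effect on the MTD therefore cannot be derived.

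What remains is that the later protections act after more patients have been exposed, the clause governing the RP2D has no criterion, and none of them revises escalation between Phase I levels.

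**Conclusion.** The point holds in a limited form. The only DLT window stated is 21 days, for the single-patient steps; the tallies that fix the MTD otherwise have none; and one DLT-free patient suffices at level 0. If section 1.4 is right, cycle 1 ends at about 65–95% of plateau and averages about 38–68%, so the MTD may describe tolerability while the drug is still accumulating. If section 8.1.1 is right, there is no shortfall.

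The likely direction is toward under-counting DLTs at a level. The size is unknown, because lower exposure need not mean proportionately fewer DLTs. The percentages rest on one-compartment linear kinetics and constant dosing. Confidence is moderate while the half-life conflict is open. The change is worth making because it is cheap and the gap is visible in the protocol's own text.

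**What to change.** 1. Reconcile sections 1.4, 3.1 and 8.1.1 on half-life, time to equilibrium and length of the DLT window, and correct whichever statement is wrong.
2. State one DLT window for declaring the MTD/RP2D that fits the reconciled figures. Apply it to the 1-, 3- and 6-patient rows of the section 3.1 chart, and repeat it in section 11.1.
3. If section 1.4 stands, keep cycle 1 as the trigger for opening the next level. Before the MTD/RP2D is fixed, count in the chart's tally the DLTs seen up to the cycle 3 day 1 visit while the patient is still on the initially assigned dose. This matches section 3.1, which already assesses toxicity on the initial dose.
4. State that patients who stop early for reasons other than a DLT, or who escalate within patient, contribute data up to that point. Otherwise the declaration could wait indefinitely on a patient who can no longer complete the window.
5. State how a late DLT at a lower level is handled when a higher level is already open.

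The cost is protocol wording, about three weeks (one further 21-day cycle) before Phase II opens, and a slightly higher counted DLT rate per level. The cycle 2 and cycle 3 day 1 visits are already in the section 9 calendar. No dose is proposed or changed.

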Figure 3: Accelerated Titration Design to be adopted in Phase I. At each dose level i, one patient will be initially treated. If that patient's common toxicity criteria score, T, is at most 2 the next patient is dosed at the next higher level (i.e. add 1 to i), unless dose i is dose 0 (the highest dose tested in this study). On the other hand, if the patient's score exceeds 2, two more patients are treated at the same dose level i. If these additional two patients' scores are both at most 2, the next patient is treated at the next higher dose level (i.e. add 1 to i), unless dose i is dose 0 (the highest dose tested in this study). On the other hand, if both patients have scores higher than 2, the next patient is dosed at the next lower level (i.e. subtract 1 from i), unless dose i is dose -2 (the lowest dose tested in this study). If only one of the two has a score higher than 2, then 3 additional patients are treated at the current dose level. If at most 2 of the 6 patients treated at this dose level have scores higher than 2, then 3 additional patients are treated at the current dose level. If at most 2 of the 6 patients treated at this dose level have scores higher than 2, this dose is declared the MTD⁻

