The chart below presents the different scenarios that can occur at a particular dose level, given the number of patients treated and number of patients that experience DLT, and the actions to be taken in the phase I dose escalation part of this study. The chart, therefore, is another means of understanding the research design of the Phase I portion of this study. Based on the research design, either 1, 3 or 6 patients can be treated with a particular dose level. The action will be either to escalate to the next dose with a single patient, add new patients to the current dose level (either 2, 3 or 5), de-escalate to the next lower dose level, declare the current dose level the MTD, or finally, declare all dose levels too toxic. For example, suppose dose level -2 does not result in a DLT, then dose level -1 is given to the next patient. If the patient treated with dose level -1 has a DLT, two more patients are treated with dose level -1. If all three patients treated with dose level -1 have DLTs, the study will be continued with the reduced dose, dose level -2. Because one patient was already treated at dose level -1, 5 more patients will be treated at dose level -2. If at most 2 of the six patients treated with dose level -2 have DLTs, dose level -2 will be declared MTD.

Number of	Numb	Were there patients	Action required
patients	er of	previously treated	
treated at	DLT's	at higher dose	
dose level		level? (Y/N)	
1	0	N	If level<0, escalate and treat 1 patient on higher dose level.
			If level = 0 , declare level 0 as MTD
		Y	Treat 5 more patients with this dose level
1	1	NA*	Treat 2 more patients with this dose level
3	1	Ν	If level<0, escalate and treat 1 patient on higher dose level.
			If level = 0 , declare level 0 as MTD
		Y	Treat 3 more patients with this dose level
3	2	NA	Treat 3 more patients with this dose level
3	3	NA	Reduce dose to next lower dose level. Continue study, taking
			note of the total number of patients treated with the lower
			dose level and number of DLT's and taking corresponding
			action required.
			If current dose level is -2, terminate study for excess toxicity
6	1 or 2	NA	Declare this dose the MTD
6	3 or		Reduce dose to next lower dose level. Continue study, taking
	more		note of the total number of patients treated with the lower
			dose level and number of DLT's and taking corresponding
			action required.
			If current dose level is -2, terminate study for excess toxicity

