11. STATISTICAL CONSIDERATIONS

11.1 Study Design/Endpoints

The study is designed as a combined Phase I/II interventional non-randomized single-center study of the safety and efficacy of quinacrine in combination with capecitabine in the treatment of patients with advanced stage colorectal adenocarcinoma.

The primary aims in Phase I are to describe toxicities/adverse reactions of quinacrine treatment in combination with capecitabine in patients with advanced CRC. Simon's accelerated titration 4B design is used to determine the dose for Phase II part of the trial. This trial design will be utilized given that quinacrine has been used in the clinic for many decades. We are not anticipating additional toxicity due to the combination with capecitabine. Total Phase I enrollment will be between 3 and 18.

Figure 3 charts the accelerated titration phase I design. It indicates that at each dose level one patient will be initially treated. If that patient's common toxicity criteria score, T, is at most 2 the next patient is dosed at the next higher level. If the patient's score exceeds 2, two more patients are treated at the same dose level. If these two patients' scores are both at most 2, the next patient is treated at the next higher dose level. If both patients have scores higher than 2, the dose is de-escalated one level. If only one of *Committee 2015 For Chase Career Carter® Office of Clinical Because. All rights rearrand*

the two has a score higher than 2, then 3 additional patients are treated at the current dose level. Finally, if at most 2 patients among the 6 at this dose level have scores higher than 2, this dose is declared the MTD. When the dose is de-escalated, the number of patients treated at the lower dose level is enlarged to 6 by adding 5, if escalation from it was made using only one patient, or by adding 3, if 3 patients have been previously treated with the lower dose. The table below lists the chance of dose escalation, pesc, in terms of the underlying chance that this dose will result in a score, T > 2. For example, if the chance that T will exceed 2 is 30% the chance of escalation is 85%. The table also lists the chance of de-escalation, pdesc, in the same way, and the chance that the MTD will be decided, pstay, on first entering a dose level. The chance that a dose level will be declared MTD when being reached by de-escalation, mtddsc, is listed directly below line listing p (T>2).

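### The Phase I dosing rules contradict each other at 2 or fewer DLTs in 6 and at 3 of 3 DLTs, and the decision chart and worked example each contain a slip

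*Combined protocol and SAP*

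**What the plan says.** The Phase I rules appear in four places: the main paragraph of Section 3.1, the Figure 3 legend, the decision chart with its introductory text, and Section 11.1.

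- **Six patients, 2 or fewer DLTs.** The legend first says "If at most 2 of the 6 patients treated at this dose level have scores higher than 2, then 3 additional patients are treated" at that level. Its next sentence repeats the condition and declares the MTD. Section 11.1 gives only the second action: "if at most 2 patients among the 6 at this dose level have scores higher than 2, this dose is declared the MTD". The text above the chart limits the cohort sizes: "Based on the research design, either 1, 3 or 6 patients can be treated with a particular dose level".
- **Three patients, 3 DLTs.** The main paragraph says "If another instance of toxicity > grade 2 is observed, three additional patients will be treated at that dose level". The legend says "if both patients have scores higher than 2, the next patient is dosed at the next lower level" (unless already at level -2), and Section 11.1 says "If both patients have scores higher than 2, the dose is de-escalated one level". The chart de-escalates, or terminates the study at level -2.
- **Six patients, no DLT.** The chart's MTD row lists one or two DLTs only. The worked example covers zero as well: "If at most 2 of the six patients treated with dose level -2 have DLTs, dose level -2 will be declared MTD".
- **Worked example.** "Because one patient was already treated at dose level -1, 5 more patients will be treated at dose level -2". In the example's own story three patients, all with DLTs, had been treated at level -1, and the single patient was at level -2.

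Section 11.1 gives total Phase I enrolment as 3 to 18 and tabulates the chances of escalating, staying, de-escalating and declaring the MTD after de-escalation.

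**The concern.** These sentences tell staff whether to dose more patients at a level under suspicion, and no text says which version controls. The chart is introduced only as another way to understand the design.

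The 3-of-3 conflict matters most. Three DLTs already exceed the limit of 2 in 6, so three further patients at that level cannot change the decision. They would be exposed at a level that has already failed.

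The legend sentence would take a level to nine patients. No rule covers nine, and total enrolment could exceed the stated maximum.

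The chart row and the worked example are label slips. They add to the confusion but leave no outcome in real doubt.

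**Working it through.** **Inputs.** The rules are those of the chart and Section 11.1. Let p be the chance of a DLT at a level and q = 1 - p. The documents give no DLT rates by level, so the trial-wide results use three assumed sets for levels -2/-1/0: 10/10/10%, 10/20/30% and 20/30/40%.

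**1. Reproduce the Section 11.1 table.** On first entry to a level:

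- Escalate: q + pq². At p = 0.3: 0.7 + 0.3 × 0.49 = 0.847.
- Stay (MTD): 2p²q⁴. At p = 0.3: 2 × 0.09 × 0.2401 = 0.043.
- De-escalate: p³ + 2p²q(1 - q³). At p = 0.3: 0.027 + 0.126 × 0.657 = 0.110.

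MTD after de-escalation to a level is [q·P(Bin(5,p) ≤ 2) + pq²·P(Bin(3,p) ≤ 1)] / (q + pq²). At p = 0.3: (0.7 × 0.8369 + 0.147 × 0.784) / 0.847 = 0.828.

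All four match the printed values, and all 36 table entries reproduce to rounding. Enumerating every path under the chart gives 3 to 18 patients, as stated.

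**2. Legend sentence (2 or fewer of 6).** The longest path under the chart is 3 at level -2, 3 at level -1, 6 at level 0 with 3 or more DLTs, 3 more at level -1 (3 or more of 6), then 3 more at level -2 with 2 or fewer of 6: 3 + 3 + 6 + 3 + 3 = 18. The legend's three more make 21.

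**3. 3 of 3 DLTs.** On first entry the chance is p³: 2.7% at p = 0.3 and 12.5% at p = 0.5. Over the whole Phase I it is p₁³ + e₁p₂³ + e₁e₂p₃³, where e is the escalation chance at a level. For 10/20/30%: 0.001 + 0.981 × 0.008 + 0.981 × 0.928 × 0.027 = 0.033. Adding three patients leaves at least 3 of 6, so de-escalation follows anyway and every probability in step 1 is unchanged.

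**4. 0 of 6.** This is reached by 0 of 1, escalation, return by de-escalation, then 0 of 5. Given de-escalation to the level, the chance is q⁶ / (q + pq²) = q⁵ / (1 + pq), which is 0.590 / 1.09 = 54% at p = 0.1 and 0.328 / 1.16 = 28% at p = 0.2. At p = 0.1 the table's MTD chance is 0.990 with this outcome counted and would be 0.448 without it, so the table treats 0 of 6 as MTD.

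**Chance over the whole Phase I, by exact enumeration:**

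| Assumed DLT rates | 2 or fewer of 6 | Mean extra patients, legend sentence (3 × chance) | 3 of 3 | 0 of 6 |
|---|---|---|---|---|
| 10/10/10% | 5.0% | 0.15 | 0.3% | 0.6% |
| 10/20/30% | 22.3% | 0.67 | 3.3% | 5.3% |
| 20/30/40% | 36.8% | 1.10 | 8.3% | 6.0% |

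**The case against.** The strongest reply is that Section 11.1 states the rule clearly, the chart agrees except for the missing zero, and every printed figure follows that rule. The legend sentence ends with the same words as the sentence before it and is probably a copying duplication. Treating nine patients would mean ignoring the next sentence, the stated cohort sizes and the maximum of 18. The main paragraph of Section 3.1 is a short summary: it omits de-escalation altogether, and its reference to another instance can be read as exactly one more DLT. The chart has a row for 3 of 3. The other two slips correct themselves in context.

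Much of this stands. No design parameter, error rate or sample size is wrong, the figure of 21 describes an unlikely reading, and the last two items are typographical. What remains is that the treatment section itself carries conflicting dosing instructions with nothing to rank them. If the summary means exactly one more DLT, it gives no action for two; read literally, it doses three more patients after 3 of 3.

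**Conclusion.** The concern holds: the Phase I rules are inconsistent as written and should be corrected. The weight rests on the 3-of-3 sentence in the main paragraph of Section 3.1 and on the legend sentence. The first would add three patients at a failed level in 0.3%, 3.3% or 8.3% of trials under the three assumed sets of DLT rates. The second would add three patients in 5.0%, 22.3% or 36.8% of trials and raise the maximum from 18 to 21. These percentages depend on the assumed rates and on the sentences being followed literally. The Section 11.1 probabilities, the 3 to 18 range and the dose decision after 3 of 3 are unaffected.

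**What to change.** - In the Figure 3 legend, delete the sentence that adds 3 patients at 2 or fewer DLTs in 6, and check the flowchart against the corrected text.
- In the main paragraph of Section 3.1, split the rule: if exactly one of the two added patients has a DLT, treat three more; if both do, de-escalate, or terminate the study at level -2.
- In the chart's six-patient MTD row, list 0, 1 or 2 DLTs.
- In the worked example, change the level of the patient already treated from -1 to -2.
- State that the corrected chart controls wherever the prose differs.

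The cost is a wording amendment. The probability table and the enrolment range stay as printed.
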